
1.5 Aim of the core protocol

This document presents the core protocol for ECDC studies of CVE and IVE against symptomatic laboratory-confirmed influenza or SARS-CoV-2 infection, respectively, at primary care level. This core protocol presents the main elements for a multicentre (multi-country) study of IVE/CVE at primary care level, outlining the agreed methods for collecting data related to influenza and SARS-CoV-2 at country level, and includes a plan for the pooled analysis. The combination of data from multiple study sites will allow for studies with more statistical power to meet more specific objectives. The protocol can be implemented for either COVID-19 or influenza, or ideally both.

The proposed method is a case-control study using a test negative design. The study population consists of people of all ages, belonging to the target group for COVID-19 or influenza vaccination, presenting to primary care with symptoms of acute respiratory infection (ARI) or influenza-like illness (ILI), and no contraindication for being vaccinated with the vaccine of interest.

This protocol is adapted from the I-MOVE and I-MOVE+ generic protocols [1, 2] and the I-MOVE-COVID-19 generic protocol [3] and is written in a generic manner. The specificities of each study site's IVE and/or CVE study can be detailed in the individual site protocol annexes (Annex 5).

This core protocol, therefore, is primarily intended to guide the implementation of ECDC-funded studies. However, ECDC encourages the implementation of VE studies, using this protocol as a basis, in countries not currently planning to participate in ECDC-funded studies. The use of consistent protocols will facilitate the comparability of study results across studies, countries, and study sites.

This document presents version 1.0 of the core protocol which is an evolving document. This document will be updated and revised as necessary.

This core protocol is complemented by a questionnaire: a list of variables to be collected and their coding are available in Annex 1.

Under each paragraph, arrow marks with italicised text indicate the points that countries/study sites could further expand when creating a country-specific protocol using the core ECDC protocol.

Protocols for IVE and/or CVE studies in other settings and part of the VEBIS project, such as in hospitals or in long-term care facilities, are also available on [ECDC's website](#).

2 Objectives

2.1 Primary objective

The primary objective is to measure, for each EU/EEA primary care study site participating in IVE and CVE¹ studies, and for pooled analyses, the direct effect (effectiveness) of influenza and COVID-19 vaccines overall and by vaccine product against symptomatic laboratory-confirmed influenza or SARS-CoV-2 infection, respectively.

2.2 Secondary objectives

The secondary objectives are to measure overall and product-specific IVE and CVE against symptomatic laboratory-confirmed influenza or SARS-CoV-2 infection, by:

- risk groups (such as clinically vulnerable people, pregnant women, etc.);
- sex;
- age groups;
- specific vaccination target groups;
- calendar time;
- time since vaccination;
- vaccine schedules;
- delay between doses (if more than one dose received);
- combination of vaccine products (if applicable).

Secondary objectives include also identifying key phenotypic or genotypic evolutions that could affect vaccine performance and to estimate IVE and CVE against specific influenza (sub)clades or SARS-CoV-2 genetic variants.

- *Each study site/country to specify primary objectives of their study as measuring CVE and IVE or CVE only or IVE only.*
- *Each study site/country to specify the (additional) secondary objectives of their study.*

¹ Countries only participating in CVE can ignore references to measurement of IVE throughout the document and vice versa.

3 Methods

3.1 Study design

At study site/country level: test-negative, case-control study design in primary care setting.

At European level: test-negative, case-control study design in primary care setting using pooled data from several countries.

3.2 Study population

The study population comprises community-dwelling individuals who present to participating physicians in the primary care setting, with symptoms meeting the case definition of their influenza or COVID-19 surveillance system, with no contraindications for influenza vaccination (for IVE) or COVID-19 vaccination (for CVE).

- *Study sites/countries to describe the setting of the influenza and COVID-19 surveillance for IVE and CVE studies (number of primary care practices included, number of primary care physicians, catchment population if possible).*
- *Study sites/countries to describe target group(s) for vaccination and order/timing of vaccination (by group when known).*
- *Study sites/countries to describe the epidemiological situation (incidence, number of influenza or COVID-19 cases).*

3.3 Study period

The study period for seasonal IVE starts when the seasonal influenza vaccine of the corresponding season becomes available and the influenza season begins in the country/region, and will finish at the end of the influenza period². Cases and controls are included from the week of onset of the first influenza positive case presenting in each country-specific study.

The study period for CVE starts when the COVID-19 vaccine is available for the target group of interest in each of the participating countries and when SARS-CoV-2 is circulating. The study period is defined for each priority vaccination group, and begins for each vaccination group, when vaccination campaign in this group begins.

Physicians in participating primary care practices recruit patients and collect data throughout the year.

- *Study sites to define the beginning of the study period for the IVE/CVE study (date/month/year).*
- *Each study site specifies the date of the start of their influenza/COVID-19 vaccination campaign for each priority vaccination group, for the vaccine products used, including recommendations for delay between first, second and subsequent doses (if applicable).*

3.4 Outcomes

IVE studies

The primary outcome of interest will be PCR laboratory-confirmed influenza in symptomatic patients of all ages consulting at primary care level. The specific outcomes of interest are:

- subtype-specific laboratory-confirmed influenza A;
- laboratory-confirmed influenza B overall and, if available, by lineage (B Victoria/B Yamagata); and
- laboratory-confirmed influenza by clade/genetic variant (where possible).

CVE studies

The primary outcome of interest will be PCR laboratory-confirmed SARS-CoV-2 in symptomatic patients of all ages consulting at primary care level. Confirmation with rapid-diagnostic tests can be considered if highly specific and sensitive tests are used (see section 3.6 on 'laboratory methods').

Secondary outcomes of interest, in the same patient group at primary care level, will be genetic variants of SARS-CoV-2.

² The end of the study period could be defined as the week before two consecutive weeks of no influenza cases after the peak.

3.5 Case and control definitions

Case definitions for surveillance can vary between systems in different countries and regions. The case definitions for suspected influenza cases and COVID-19 cases in this protocol are suggestions and can be adapted to the study site-specific surveillance protocols. Collecting detailed symptom information allows reconstitution of case definitions among data collected, if initial case definitions are sensitive.

3.5.1 General case definitions

Within the EU, standard surveillance case definitions have been established for influenza-like illness (ILI) or acute respiratory infection (ARI) [20].

An ILI patient is defined as an individual who consults a participating physician, presenting with sudden onset of symptoms AND at least **one** of the following four systemic symptoms:

- Fever or feverishness
- Malaise
- Headache
- Myalgia

AND at least **one** of the following three respiratory symptoms:

- Cough
- Sore throat
- Shortness of breath

An ARI patient is defined as an individual who consults a participating physician, presenting with sudden onset of symptoms AND at least **one** of the following four respiratory symptoms:

- Cough
- Sore throat
- Shortness of breath
- Coryza

AND a clinician's judgment that the illness is due to an infection.

3.5.2 Case definitions for IVE study

A **suspected influenza case** will be a patient meeting the EU ILI case definition or the EU ARI case definition [20].

A **confirmed influenza case** in the context of this study will be defined as a suspected influenza case with a respiratory sample PCR-positive for influenza virus. Only symptomatic patients (suspected influenza cases) are included.

An **influenza negative patient (a test-negative control)** will be defined as a suspected influenza case with a respiratory sample PCR-negative for influenza virus.

In the context of integrated influenza and COVID-19 surveillance, either an ILI or an ARI case definition can be used to select patients for swabbing and, if symptoms are collected with high quality, in the analysis the symptom information can be used to restrict to patients meeting the EU ILI case definition.

3.5.3 Case definitions for CVE study

A **suspected COVID-19 case** will be someone meeting the EU ARI case definition [20].

A **confirmed COVID-19 case** in the context of this study will be defined as a suspected COVID-19 case with a respiratory sample PCR-positive for SARS-CoV-2. Only symptomatic patients (suspected COVID-19 cases) are included.

A **COVID-19 negative patient (a test-negative control)** will be defined as a suspected COVID-19 case with a respiratory sample PCR-negative for SARS-CoV-2.

Other case definitions could be considered in the context of the study site-specific respiratory pathogen surveillance.

- *Each study site to indicate which case definitions they will use for the IVE and CVE study.*

3.5.4 Other control groups (optional)

In addition, an analysis with different control groups will be carried out. The default control group will be those patients testing PCR-negative to influenza (for IVE studies) or SARS-CoV-2 (for CVE studies). Other control groups will include (where this information is available):

- Patients testing PCR-negative to all respiratory viruses.
- Patients testing PCR-positive to respiratory viruses other than influenza (if IVE) or SARS-CoV-2 (if CVE), for example: rhinovirus, RSV, etc (noting that patients with seasonal coronaviruses are excluded for CVE).
- Patients attending general practitioner (GP) practices for reasons other than a respiratory infection (a traditional case control study) could also be considered, particularly during periods where there may be low circulation of other respiratory viruses (more relevant for CVE).

In the context of a high correlation between influenza and COVID-19 vaccination, control groups can exclude SARS-CoV-2 PCR-positive patients (IVE) or influenza PCR-positive patients (CVE), see section 5.1.7.

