3.8 Exposure (vaccination)

3.8.1 Definition of vaccination status

Current seasonal influenza vaccine

An individual is considered as:

- vaccinated against influenza if they received one dose of the (product-specific) current season influenza vaccine 14 or more days before disease onset;
- unvaccinated if they
- unvaccinated if they:
 - did not receive influenza vaccine in the current season; or
 - received one dose of the (product-specific) current season influenza vaccine less than 14 days before disease onset; or
 - were vaccinated after their symptom onset date.

Current pandemic COVID-19 vaccine

COVID-19 vaccination rollout schedules are evolving and this section will need to be updated on an ongoing basis to reflect any new vaccination schedules.

An individual will be considered as vaccinated against COVID-19 with a product-specific vaccine under the following categories:

- **Fully vaccinated with a primary course, first booster plus second booster:** Patients will be considered fully vaccinated with second booster if they have **received completed primary course vaccination plus booster (see below) followed by a second booster dose** at least 14 days* before symptom onset.
- **Fully vaccinated with a primary course plus booster:** Patients will be considered fully vaccinated with booster if they have **received completed primary course vaccination (see below) followed by a booster dose** at least 14 days* before symptom onset.

- **Fully vaccinated with a primary course** (two-dose vaccine): Patients will be considered fully vaccinated if they have **received both doses** at least 14 days⁵ before symptom onset.
- **Fully vaccinated with a primary course** (single-dose vaccine): Patients will be considered fully vaccinated if they have **received one dose** at least 14 days⁵ before symptom onset.
- **Partially vaccinated** (two-dose vaccine only): Patients will be considered partially vaccinated if they have **received one of two doses** at least 14 days⁵ before symptom onset.
- Patients will be considered as **unvaccinated** if they **did not receive COVID-19 vaccine** or if they **were vaccinated after onset** of symptoms.

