3.8.2 Vaccination status ascertainment

The exposure of interest in this study is a vaccination history with influenza vaccine or COVID-19 vaccine. The vaccination history includes date of administration, vaccine product and brand name, and the number of doses received (if applicable). Documenting the batch codes (where this is feasible) will allow identification of the vaccine brand, the vaccine content and the dose.

An individual is considered as vaccinated if they meet at least one of the following criteria:

- they are registered as vaccinated in a vaccination registry (preferred option);
 - they self-report having received an influenza or COVID-19 vaccination;
 - they are registered as vaccinated against influenza or COVID-19 in the GP information system;
 - their insurance company can show evidence of pharmacy delivery or re-imburement of influenza or COVID-19 vaccine/vaccination;
 - influenza or COVID-19 vaccination has been recorded in their vaccination card/vaccination booklet.
- *Each study site to document:*
- *the vaccine products used;*
 - *places of vaccination (GPs, specific vaccination centres, etc.);*
 - *the precise mode of vaccine ascertainment (self-report, card, registry, etc.);*
 - *if no precise dates of vaccination are collected, the variable allowing a patient to be defined as vaccinated or unvaccinated;*
 - *vaccine status ascertainment validation;*
 - *potential limitations of the vaccine status ascertainment.*

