A multivariable logistic regression analysis will be conducted to estimate VE and control for negative and positive confounding. Odds ratios and standard errors will be obtained. Variables will be tested for multicollinearity. Interactions will be tested using the likelihood ratio test or Wald's test and will be included in the model if significant at the 5% level. Factors other than statistical significance (prevalence of exposure, magnitude of OR/VE, biological plausibility) will also be used as criteria for inclusion of a variable or an interaction term. As noted in the 'Pooled crude VE estimates' section, study site and onset time should always be controlled for in each model.

Variable selection and model specification

Model development strategy

To find a suitable model, we will consider very carefully the variables collected and determine which are GP level variables, which are individual level variables, which variables are mediators of each other, and which variables are

potential confounders and effect modifiers. Variables will also be checked for collinearity, and decisions will be made to include the group of collinear variables in the model or select among them.

The above considerations are particularly important for this study, as some of the medication information collected and the chronic conditions of the patients may be strongly correlated.

Creating a direct acyclical graph may help better understand the relation between all variables collected and the outcomes.

Some variables will be a priori variables. These are variables that we want to keep in the model, as previous studies have shown them to be potential confounders or effect modifiers. These could include age and sex, but also potentially others.

If the model is not overfitted and variables are included that are not collinear or mediators, then there may be less concern for parsimony, as including insignificant variables may result in more accurate p -values for tests for variables of interest.

However, if sample size is low and the model is overfitted, then a backwards step-down variable selection procedure could be considered.

Interaction terms should be included cautiously, factors other than statistical significance (prevalence of exposure, magnitude of OR) will also be used as criteria for inclusion of an interaction term.

Several different models may have to be presented and considered.

Continuous variables

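### The optional non-respiratory GP control group does not exclude visits made to be vaccinated, and has no date to stand in for symptom onset

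*Protocol*

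**What the plan says.** Section 3.5.4 names the main control group first: "The default control group will be those patients testing PCR-negative to influenza (for IVE studies) or SARS-CoV-2 (for CVE studies". It then lists alternatives, the third being: "Patients attending general practitioner (GP) practices for reasons other than a respiratory infection (a traditional case control study) could also be considered". It suggests this group "particularly during periods where there may be low circulation of other respiratory viruses (more relevant for CVE"). The bullet puts no limit on the reason for the visit beyond its not being respiratory.

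Section 3.8.2 asks each site to document "places of vaccination (GPs, specific vaccination centres, etc.)", so vaccination at the GP practice is foreseen.

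Exposure is dated from illness. For IVE, section 3.8.1 counts a person as "vaccinated against influenza if they received one dose of the (product-specific) current season influenza vaccine 14 or more days before disease onset", and as unvaccinated if they "received one dose of the (product-specific) current season influenza vaccine less than 14 days before disease onset". For CVE, the vaccinated categories require the dose or doses "at least 14 days* before symptom onset" (or the same with a footnote mark). Section 3.7.3 removes from the main analysis patients whose latest dose fell 1–13 days before onset. Annex 4 adds that "study site and onset time should always be controlled for in each model", and section 5.1.8 likewise names onset date as the time adjustment.

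**The concern.** A control group should reflect how common vaccination is in the population that produced the cases. If some controls are in the practice because they came for the vaccine, they are sampled on the exposure itself. The protocol accepts this principle elsewhere. Section 3.7.3 drops controls positive for a seasonal coronavirus because vaccination may affect them, and section 5.1.7 calls independence of the control group from the vaccination a key prerequisite of the test-negative design.

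Separately, a patient attending for, say, a sprain has no onset date, so the exposure rule, the recent-dose exclusion and the time term have nothing to run from. Two sites could date and code the same patients differently. A gap between this estimate and the test-negative one would then be hard to interpret, although that comparison is the reason for having a second control group.

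**Working it through.** **Is there a rule elsewhere that closes the gap?** No.
- Section 3.7.1 defines participants as symptomatic patients and gives no separate definition for this group.
- Section 3.7.3 has no exclusion by reason for visit.
- Section 3.9.2 collects the type of consultation only.
- Annex 1 lists onset date and swab date, but neither a consultation date nor a reason for visit.
- The Annex 5 checklist does not ask sites how these controls are selected or dated.

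**How is a dose given at the index visit classified?** Take the visit date as index.
- IVE: a dose on day 0 is less than 14 days before the index date, so the patient is unvaccinated under 3.8.1. The exclusion in 3.7.3 covers days 1–13 and does not remove day 0.
- CVE: the dose is not at least 14 days old, the patient is not without vaccine, and the dose was not given after onset. No 3.8.1 category fits that dose. Someone attending for a booster keeps the category earned by earlier doses.

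**A scale for the effect, from Table 4.** The row with OR 0.5, control coverage 0.5 and lower-limit precision 0.2 states 289 cases, 289 controls and a CI of 30–64. Using n = [1/(p1·q1) + 1/(p0·q0)] / [ln((OR + d)/OR)/1.96]², with p0 = 0.5 and p1 = 0.5/1.5 = 1/3:
- numerator: 4.5 + 4 = 8.5
- denominator: (ln 1.4/1.96)² = (0.3365/1.96)² = 0.02947
- n = 8.5/0.02947 = 288.4, rounded up to 289; the interval with 289 per group is 30.0–64.3. The row is reproduced.

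**Size of the distortion, IVE.** Let c be the true coverage and f the share of these controls who came to be vaccinated. The documents do not give f, so it is an assumption. Case exposure odds are (1 − VE)·c/(1 − c). Control coverage becomes c(1 − f), and estimated VE = 1 − case odds/control odds.

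For true VE 50%, c = 0.5 and f = 10%: case odds 0.5; control coverage 0.45; control odds 0.45/0.55 = 0.818; OR = 0.5/0.818 = 0.611; VE = 38.9%. The same steps give:

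| True coverage | f = 5% | f = 10% | f = 20% |
|---|---|---|---|
| 30% | 46.2% | 42.1% | 32.1% |
| 50% | 44.7% | 38.9% | 25.0% |
| 70% | 41.2% | 31.5% | 8.3% |

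At 50% coverage, a 20% share takes the estimate below the Table 4 interval of 30–64.

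**CVE.** If a site codes the same-day dose as vaccinated, control coverage is c(1 − f) + f. At c = 0.5, shares of 5%, 10% and 20% then give VE of 54.8%, 59.1% and 66.7%, which is too high. Coded as unvaccinated, the 50% row of the table applies. For overall CVE against the unvaccinated, booster visitors keep an earlier vaccinated category, so the c(1 − f) model does not describe them.

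**The case against.** The best defence is that the group is optional, that another group is the default, and that this is a generic core protocol whose site details go to annexes. An index date and a screen on visit reason could be supplied there or in an analysis plan. The shares and their effect are assumed, and no passage shows that periods of low virus circulation coincide with vaccination campaigns. All of this limits the weight of the point. It does not remove it. The bullet as worded admits vaccination visits, Annex 4 is itself the detailed pooled plan and demands onset time in each model, and a later plan cannot recover a visit reason or date that was never collected.

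A reader might also infer a second bias. If controls are dated at the visit and cases at onset, controls seem to gain days in which to be vaccinated, which would push VE up. A crude calculation gives that impression. With coverage rising from 30% by 0.5–1 point a day and a lag of 3–4 days, control coverage is 31.5–34% and a true VE of 50% reads as 53–58%. The documents do not support this for the adjusted estimate. Sections 5.1.8 and Annex 4 require a time term. If each patient's own index date serves for both exposure and time, cases and controls are compared on the same calendar day. Coverage is then the same c(t) for both, and the OR is 0.5 again, provided the time term is flexible enough.

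Nor is exposure undatable throughout. Never-vaccinated patients and those vaccinated long before can be classified, so the difficulty concerns mainly recent doses. The 60-day rule on previous SARS-CoV-2 infection is worded in section 3.9.8 without reference to onset.

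**Conclusion.** The point holds in a limited form. As written, the non-respiratory GP control group can include people who attend to be vaccinated, and it has no date to replace symptom onset in rules that depend on it. For IVE, with visit date as index, the bias is downward: a true VE of 50% at 50% coverage reads as about 45%, 39% or 25% for assumed vaccination-visit shares of 5%, 10% or 20%. For CVE the direction depends on how a same-day dose is coded, so a general claim that VE is too low would go too far. The size rests wholly on the assumed share and on coverage among the other controls equalling that of the source population. The default test-negative estimates are untouched, and a reader should not take this as a flaw in the primary analysis.

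**What to change.** - In the third bullet of section 3.5.4, add the words *or vaccination* after the respiratory-infection exception, so that visits made to be vaccinated do not qualify.
- State that for these controls the consultation date takes the place of onset date in the exposure and exclusion rules and in the time term, while cases keep their onset date. Cases should not be moved to consultation or swab date. A case vaccinated 12 days before onset and swabbed 3 days after it would be 15 days from vaccination at the swab and would count as vaccinated, whereas section 3.7.3 excludes that case from the main analysis. Case exposure would then differ between the two comparisons.
- Add consultation date and reason for visit to Annex 1 for these controls only.

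The cost is some wording and two variables at sites that use the group. The downside is fewer eligible control visits in campaign weeks. Nothing changes in the default test-negative analysis.
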